| 4.16. | Lid wiper Epitheliopathy | Record the lid wiper epitheliopathy (upper & lower) by Lissamine green, OD & OS | Lid Wiper Epitheliopathy Work Aid (Appendix H) |
| 4.17. | Conjunctival staining | Record the conjunctival staining by Lissamine green, OD & OS | |
| 4.18. | Meibomian Gland Expressibility (Lower lid, 3 regions) | Record the Meibomian Gland Expressibility, OD & OS via Meibomian Gland Secretion Grading Scale (Appendix I) | Procedure per Meibomian Gland Evaluator manufacturer instructions. (Appendix I) |
| 4.19. | Eye Rinse | If the clearance of dye needs to be expedited, the study investigator or technician will rinse the subject's eyes thoroughly with a study provided solution. | |

FINAL EVALUATION

The final evaluation will ordinarily take place immediately following the last scheduled follow-up visit per the study protocol. It may also take place at any point the subject discontinues the study or is terminated from the study.

| Final Evaluation | | |
|------------------|---|---|
| Step | Procedure | Details |
| F.1 | Final Exam Form | Indicate if the subject completed the study successfully. If subject discontinued from the study, indicate the reason. |
| F.2 | Sensitivity Questionnaire | Completed subjects will respond to a Sensitivity Questionnaire |
| F.3 | Subjective spherocylindrical Refraction | Perform bare-eye subjective spherocylindrical refraction with a phoropter and record the best corrected distance Snellen visual acuity to the nearest letter (OD, OS). |
| F.4 | Exit Slit Lamp Biomicroscopy | For discontinued subjects, FDA Slit Lamp Classification Scale will be used to grade the findings. If the clearance of dye needs to be expedited, preservative-free rewetting drops or saline may |

| Final Evaluation | | | |
|------------------|-----------|---------------|--|
| Step | Procedure | Details | |
| | | be instilled. | |

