| Exit Snellen Distance Visual Acuity | x | x | | x | |
| Dispense Patient Instruction Guide | x | | | | |
| Dispense Test Article | x | | | x | |
| Lens wear time | x | x | | | x |
| SMS text message set up | x | | | | |
| Follow-up Questionnaire | | x | | | x |
| Study Completion | | | | | x |

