| 1.26 | Spectacle corrected Visual Acuity | 
Record the distance and near Snellen visual acuity (OD, OS) to the nearest letter. Subjects must read the smallest line until at least 50% of the letters are read incorrectly.
 
Near (40 centimeters):
 
 • Early Treatment Diabetic Retinopathy Study (ETDRS) 2000 Series (charts 1, 2). 
Snellen visual acuity at distance and near must be within 1 line between subject's own spectacle and the manifest refraction, distance and near, OD & OS to continue.
 |
| 1.27 | Eligibility after Baseline | 
All responses to Inclusion Criteria questions must be answered "yes" and all responses to Exclusion Criteria questions must be answered "no" for the subject to be considered eligible.
 
If a subject is deemed to be ineligible after baseline, proceed to Final Evaluation and complete all forms.
 |
| 1.28 | Randomization (if applicable) | If a subject is enrolled into the interventional arm, they will be randomized per the randomization scheme. |
| 1.29 | Treatment Selection (if applicable) | Assign the treatment based on the randomization scheme. Subjects assigned spectacle wear will continue to step 1.30. Subjects assigned contact lens wear will continue to Step 1.32 |
| 1.30 | SMS text message set up | Text message program will be set up and subject will be instructed on use. They will provide the average time they stop using their glasses/contact lenses each evening and the text message will be set to be sent 30 minutes prior to that time. |
| 1.31 | Subject instruction | The subjects will be scheduled for Visit 2 in |

| Visit 1: Baseline | | |
|-------------------|-----------|---|
| Step | Procedure | Details |
| | | 6-8 days and will present after at least 6 hours of spectacle wear on the day of the visit. |

| Visit 1: Treatment 1 (Study lens fitting) | | |
|---|--|---|
| Step | Procedure | Details |
| 1.32 | Lens Insertion | Select the contact lens power based on subjective best sphere refraction. The subject inserts the study lenses. Record the time of lens insertion. Check for lens damage under the slit lamp before proceeding with lens settling. Replace damaged lenses if applicable. |
| 1.33 | Lens Settling | Allow the study lenses to settle for a minimum of 5 minutes. |

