| 3.3. | Visual Acuity | Record the distance Snellen distance visual acuity with the contact lenses (OD, OS) to the nearest letter. Subjects must read the smallest line until at least 50% of the letters are read incorrectly. |
| 3.4. | Habitual lens Pre-Lens Tear film stability as available by site | Record the first tear film stability (NIBUT/NIKBUT), OD & OS. Record three measurements. |
| 3.5. | Habitual lens Wettability Characteristics | Record the white light lens wettability of both lenses. |
| 3.6. | Habitual Lens Surface Debris & Deposits | Record any front and back surface lens debris and deposits. |
| 3.7. | Lens Removal and Storage | If present, the lenses will be removed by the subject and stored in appropriate solution or discarded if appropriate. |
| 3.8. | Slit Lamp Biomicroscopy | FDA Slit Lamp Classification Scale will be used to grade the findings and determine eligibility. If the subject has a Grade 3 slit lamp finding, it will be recorded as an Adverse Event |
| 3.9. | Lid wiper Epitheliopathy | Record the lid wiper epitheliopathy (upper & lower) by Lissamine green, OD & OS |
| 3.10. | Conjunctival staining | Record the conjunctival staining by Lissamine green, OD & OS |
| 3.11. | Eye Rinse | If the clearance if dye needs to be expedited, the study investigator or technician will rinse the subject's eyes thoroughly with a study provided solution. |

| Visit 3: Treatment 2 | | |
|----------------------|--|--|
| Step | Procedure | Details |
| 3.12. | Continuance | Confirm subject eligibility |
| 3.13. | Treatment Selection | Assign the treatment based on the randomization scheme. Select the contact lens power based on subjective best sphere refraction. |
| 3.14. | Spectacle corrected Exit Visual Acuity | For Subjects wearing spectacles record the distance Snellen visual acuity (OD, OS) to the nearest letter. Subjects must read the smallest line until at least 50% of the letters are read incorrectly. |
| 3.15. | Spectacle corrected Subject instruction | The spectacle corrected subjects will be scheduled for Visit 4 in 6-8 days and will present after at least 6 hours of spectacle on the day of the visit. Subjects instructed to continue to participate in the SMS text messaging questionnaire. |
| 3.16. | Lens Insertion (if applicable) | The subject inserts the study lenses. Record the time of lens insertion. Check for lens damage under the slit lamp before proceeding with lens settling. Replace damaged lenses if applicable. |

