| 3.25. | Dispense (if applicable) | 
The lenses will be dispensed for a 6-8 day wearing period. During this time, they are required to wear the lenses at least 5 days and at least 8 hours per day that they are worn.
 
 • Dispense enough lenses to last the subject to their scheduled follow-up visit. Do not dispense extras* • The lenses will be worn as daily wear/daily disposable only • A patient instruction booklet will be provided • Subjects will be scheduled for their 1-week follow-up visit, ensuring that they wear the study lens at least 6 hours on the day of the follow-up visit 
* Note: In the event a lens is lost or damaged, the subject will return to the clinical site for replacement. As much as reasonably
 | |

| Visit 3: Treatment 2 | | |
|----------------------|---------------------|--|
| Step | Procedure | Details |
| | | possible, a damaged lens and packaging should be returned to the clinical site (wet, if possible) and then returned to the Sponsor. If lens damage is present, complete the Product Quality Complaint Form. The lens will be stored in labeled vial with saline, and clearly differentiated from the other worn lenses that will be shipped back to the Sponsor. |
| 3.26. | Subject instruction | The subjects will be scheduled for Visit 4 in 6-8 days and will present after at least 6 hours of spectacle or contact lens wear time (as assigned) on the day of the visit. |

VISIT 4

The subjects must present to Visit 4, 6-8 days following Visit 3, after at least 6 hours of wear time on the day of the visit.

| Visit 4: Treatment 2 Follow-Up 1 | | |
|----------------------------------|---|---|
| Step | Procedure | Details |
| 4.1. | Adverse Events and Concomitant Medications Review | Review any changes to the subject's medical history or concomitant medications from the previous study visit. Record any changes, and any adverse events. |
| 4.2. | Wearing Time (if applicable) | Record the average wearing time and comfortable wearing time. |
| 4.3. | Compliance | Confirm compliance with the prescribed wear schedule. |
| 4.4. | Subject Reported Ocular Symptoms | Subjects will respond to a verbal open-ended symptoms questionnaire. |
| 4.5. | Follow-Up Spectacle Questionnaires (if applicable): DEQ-5, MRD, and Digital Device | The subject will respond to the Follow-Up Questionnaire. |

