15. DATA HANDLING AND RECORD KEEPING/ARCHIVING

15.1. Electronic Case Report Form/Data Collection

The data for this study will be captured on electronic case report forms (eCRFs) using an EDC system (Bioclinica). An authorized data originator will enter study data into the eCRFs using the EDC system. Data collected on equipment that is not captured in EDC will be formatted to the specification of the JJVC database manager and sent to JJVC for analysis.

External Date Sources for this study include: Nightly text messaging comfort scores. These will be analyzed by the sponsor and included in the CSR.

The clinical data will be recorded on dedicated eCRFs specifically designed to match the study procedures for each visit. Once completed, the eCRFs will be reviewed for accuracy and completeness and signed by the Investigator. The sponsor or sponsor's representatives will be authorized to gain access to the subject recordation for the purposes of monitoring and auditing the study.

Edit checks, electronic queries, and audit trails are built into the system to ensure accurate and complete data collection. Data will be transmitted from the clinical site to a secure central database as forms are completed or updated, ensuring information accuracy, security, and confidentiality. After the final database lock, the Investigator will be provided with Individual Patient Profiles (IPP) including the full audit trail on electronic media in PDF format for all of the study data. The IPP must be retained in the study files as a certified copy of the source data for the study.

The content and structure of the eCRFs are compliant with ISO14155:2011.¹

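### The nightly comfort text is timed once, at Visit 1, from a stop time whose correction is not named, and no Visit 3 step re-times it at crossover

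*Combined protocol and SAP*

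**What the plan says.** After treatment assignment at Visit 1 (section 7.2, step 1.29) the interventional arm splits. "Subjects assigned spectacle wear will continue to step 1.30", which sets up the texting programme; lens-first subjects go to 1.32 and reach the same set-up at 1.42. The two set-up steps are worded identically. On the stop time, both say: "They will provide the average time they stop using their glasses/contact lenses each evening". Scheduling then follows from that single answer, since under either step "the text message will be set to be sent 30 minutes prior to that time".

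In Table 4 (section 7.1) the row "SMS text message set up" is marked at Visit 1 only. At Visit 3, step 3.13 assigns the period-2 treatment. Step 3.15, for subjects moving to spectacles, adds "Subjects instructed to continue to participate in the SMS text messaging questionnaire". The lens steps from 3.16 onward do not mention texting, and the closing step 3.26 covers only the Visit 4 appointment and the need to "present after at least 6 hours of spectacle or contact lens wear time (as assigned) on the day of the visit".

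Section 15.1 names "Nightly text messaging comfort scores" as an external data source that the sponsor will analyse and report. Section 2.2 lists 0-100 subjective comfort among the other exploratory endpoints, and section 14.7 compares these endpoints descriptively between Test lens and Spectacles.

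**The concern.** The 30-minute lead has one evident purpose: to obtain a rating late in the day while the correction is still being worn. That works for the correction whose stop time was given. In a crossover the same subject later wears the other correction, and lenses and spectacles need not come off at the same hour. Subjects must own usable spectacles and have about -2.00 to -6.00 D of myopia (section 3.2, criteria 8 and 9). It is therefore plausible, though not documented, that many take lenses out and finish the evening in glasses.

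At stake is whether the two comfort scores being compared were taken at comparable points of wear. A subject prompted too late in a lens period could be rating with no lens on the eye, possibly while wearing the comparator. A subject prompted too early in a spectacle period would be rating less of the day. These are different kinds of error, so averaging over the two sequences cannot be relied on to cancel them. None of the visit steps records whether the correction was on when the subject replied, so mistimed ratings might not be identifiable afterwards.

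**Working it through.** The plan states no figure on this point, so there is nothing to reproduce. The check is a reading of every texting step, followed by the timing arithmetic.

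**Steps side by side**

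| | Spectacles first | Lens first |
|---|---|---|
| Set-up at Visit 1 | 1.30, one stop time | 1.42, same wording |
| New stop time at Visit 2, washout or Visit 3 | none | none |
| Correction worn in period 2 | Test lens | Spectacles |
| Told at Visit 3 to keep answering | no (3.16 to 3.26) | yes (3.15) |

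**Timing.** Let S be the stop time given at Visit 1, L the time at which the correction being worn actually comes off, and g = S - L in minutes. The text is sent at S - 30. Its position relative to removal is (S - 30) - L = g - 30, where a positive value means after removal.

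| g (assumed, min) | g - 30 | Text arrives |
|---|---|---|
| -60 | -90 | 90 min before removal |
| 0 | -30 | 30 min before, as intended |
| 15 | -15 | 15 min before |
| 30 | 0 | at removal |
| 45 | 15 | 15 min after |
| 60 | 30 | 30 min after |
| 90 | 60 | 60 min after |
| 120 | 90 | 90 min after |

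Any non-zero g moves the rating from its intended point. Only g above 30 puts it after removal. The documents give no value for g. Step 3.25 asks for at least 8 hours of lens wear on worn days, so a large gap is permitted, but nothing shows that one occurs.

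**Which period is affected depends on what S means.**

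- If S is for the assigned first correction (suggested by where the set-up steps sit), period 1 is timed as intended and period 2 may not be, in both sequences. With lenses coming off earlier than spectacles, spectacle-first subjects would be texted late in their lens period, and lens-first subjects early in their spectacle period.
- If S is for the habitual contact lens, the lens period is timed about as intended, provided test-lens removal follows habit. The spectacle period may be mistimed in either sequence, so the mismatch would follow the treatment.

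Under both readings one fixed time serves two corrections, and the wording does not settle which reading is meant.

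**The case against.** The strongest counter-argument is that a single clock time is a reasonable choice: it holds time of day constant across the two periods, whereas a reset would let clock time differ by condition. The trade-off is real and should be accepted openly. It does not rescue the current text, because the protocol ties the prompt to when the correction is taken off, not to a fixed hour, and the plan can break that rule at crossover.

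A reader might infer that period-2 lens comfort will be rated after lens removal for half of the interventional arm, by 0.5 to 2.5 hours, every night. The documents do not support that. The range comes from assuming a gap of 1 to 3 hours and leaves out gaps of 0 to 30 minutes, where the text arrives before or at removal. Lenses are required on at least 5 days of a 6-8 day period, not every night. The premise that S refers to the first correction is an inference from branch position; these subjects are habitual lens wearers, and an established average could well be their habitual lens time.

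A reader might also infer that the one-sided reminder in 3.15 biases response rates. That is too strong. The text is itself the nightly prompt, both branches are instructed on its use at Visit 1, and no step stops it for anyone. The missing line in 3.26 is an omission to tidy.

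Two further points stand. Appendix A is blacked out and the Patient Instruction Guide is provided separately, so the text item may already ask about comfort during wear or whether the correction is on. And Table 4, as read here, does not match the visit steps everywhere (lid wiper assessment at Visit 3, step 3.9, is not marked), so the blank cells in its texting row are weak evidence. The detailed steps carry the point.

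**Conclusion.** The gap holds as a matter of procedure: one stop time, not tied to a named correction, is collected at Visit 1 and not re-collected when the correction changes. When a subject's lens and spectacle stop times differ by more than 30 minutes, the rating in one of the periods can be requested after the correction is off, or at a materially different point before removal. The size and direction of any effect on the Test-Spectacles comfort difference cannot be stated from the documents.

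The consequence is limited. Comfort is one of several exploratory endpoints, analysed descriptively, in a study that section 2.3 calls a pilot. NIBUT/NIKBUT and the secondary endpoints do not depend on the text. This is a worthwhile, low-cost improvement, not a threat to the study's main conclusion. The conclusion assumes that sites follow the written steps; a site could adjust the time informally, but nothing in the visible text requires it.

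**What to change.** 1. In 1.30 and 1.42, state that the stop time is for the correction assigned for the coming period.
2. Add a Visit 3 step for both sequences that re-collects the average stop time for the period-2 correction and resets the text to 30 minutes before it.
3. Mark that step at Visit 3 in Table 4.
4. Repeat in 3.26 the instruction from 3.15 to keep answering texts.

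Optionally, if the text item does not already ask, record whether the assigned correction was on at the time of reply. A reset based on an average time cannot guarantee that.

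The cost is an estimated minute per subject at Visit 3, so about 46 minutes in all if all 46 interventional subjects in Table 1 (23 + 23) reach it, plus a few lines of protocol text. The one real downside is that the clock time of the rating may then differ between a subject's two periods. Recording the send time would let the report show by how much.

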| 2.4. | Subject Reported Ocular Symptoms | Subjects will respond to a verbal open-ended symptoms questionnaire. | |
| 2.5. | Follow-Up Spectacle Questionnaires (if applicable): DEQ-5, MRD, and Digital Device | The subject will respond to the Follow-Up Questionnaire. | |
| 2.6. | Follow-Up Contact lens Questionnaires (if applicable): CLDEQ-8, MRD, and Digital Device | The subject will respond to the Follow-Up Questionnaire. | |
| 2.7. | Visual Acuity | Perform monocular distance and near ETDRS LogMAR visual acuity test, OD & OS | |
| 2.8. | Subjective Lens Fit | Evaluate overall lens fit acceptance | |

| Visit 2: Treatment 1 Follow-Up 1 | | |
|----------------------------------|--|--|
| Step | Procedure | Details |
| | Assessment (if applicable) | 
(acceptable or unacceptable) based on centration, movement and other fitting characteristics.
 
An unacceptable fit is deemed by one of the following criteria:
 
 • limbal exposure at primary gaze or with extreme eye movement • edge lift • excessive movement in primary and up gaze • insufficient movement in all three of the following conditions: primary gaze, up gaze, and Josephson push up 
Note: if lens fit is unacceptable subject will be discontinued from the study.
 |
| 2.9. | Wettability Characteristics (if applicable) | Record the white light lens wettability of both lenses. |
| 2.10. | Surface Debris & Deposits (if applicable) | Record any front and back surface lens debris & deposits. |
| 2.11. | Tear film stability (Pre-Lens or Pre-Corneal as applicable) | Record the first tear film stability (NIBUT/NIKBUT), OD & OS. Record three measurements. |
| 2.12. | Blink patterns (as site applicable) | Record the Blink Patterns, OD & OS |
| 2.13. | Pre-corneal or Pre-lens (as applicable) tear film lipid layer thickness as available by site | Record the tear film lipid layer thickness, OD & OS |
| 2.14. | Lens Removal and Storage (if applicable) | 
The lenses will be removed by the subject. VRC site only, both lenses will be stored dry in a labeled glass vial and frozen, using study specific labels.
 
Otherwise, lenses will be discarded.
 |
| 2.15. | Slit Lamp Biomicroscopy | FDA Slit Lamp Classification Scale will be used to grade the findings and determine eligibility. |

| Visit 2: Treatment 1 Follow-Up 1 | | | |
|----------------------------------|---|---|---|
| Step | Procedure | Details | |

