| 4.6. | Follow-Up Contact lens Questionnaires (if applicable): CLDEQ-8, MRD, and Digital Device | The subject will respond to the Follow-Up Questionnaire. |
| 4.7. | Visual Acuity | Perform monocular distance and near ETDRS LogMAR visual acuity test, OD & OS |
| 4.8. | Subjective Lens Fit Assessment (if | Evaluate overall lens fit acceptance (acceptable or unacceptable) based on |

| Visit 4: Treatment 2 Follow-Up 1 | | | |
|----------------------------------|--|---|--|
| Step | Procedure | Details | |
| | applicable) | 
centration, movement and other fitting characteristics.
 
An unacceptable fit is deemed by one of the following criteria:
 
 • limbal exposure at primary gaze or with extreme eye movement • edge lift • excessive movement in primary and up gaze • insufficient movement in all three of the following conditions: primary gaze, up gaze, and Josephson push up 
Note: if lens fit is unacceptable subject will be discontinued from the study.
 | |
| 4.9. | Wettability Characteristics (if applicable) | Record the white light lens wettability of both lenses. | |
| 4.10. | Surface Debris & Deposits (if applicable) | Record any front and back surface lens debris and deposits. | |
| 4.11. | Tear film stability (Pre-Lens or Pre-Corneal as applicable) as available by site | Record the first tear film stability (NIBUT/NIKBUT), OD & OS. Record three measurements. | (Appendix E & F) |
| 4.12. | Blink patterns (as site applicable) | Record the Blink Patterns, OD & OS | Lipiview II manufacturer instructions (Appendix G) |
| 4.13. | Pre-corneal or Pre-lens (as applicable) tear film lipid layer thickness as available by site | Record the tear film lipid layer thickness, OD & OS | Lipiview II manufacturer instructions (Appendix G) |
| 4.14. | Lens Removal and Storage (if applicable) | 
The lenses will be removed by the subject. VRC site only, both lenses will be stored dry in a labeled glass vial and frozen, using study specific labels.
 
Otherwise, lenses will be discarded.
 | |
| 4.15. | Slit Lamp Biomicroscopy | FDA Slit Lamp Classification Scale will be used to grade the findings | |

| Visit 4: Treatment 2 Follow-Up 1 | | | |
|----------------------------------|---|--|---|
| Step | Procedure | Details | |
| | | If the subject has a Grade 3 slit lamp finding, it will be recorded as an Adverse Event | |

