Adjust the camera to the proper focus. The screen will prompt which corrections need to be made to reach the proper orientation. Once aligned and focused there will be a prompt to instruct the patient to blink 2 times. Ask the patient to complete 2 full blinks and then hold their eye open as wide as they can for as long as they can. The instrument will start recording automatically and will stop when the patient blinks, or when there is extreme tear break up, or after 25 seconds. After conducting a NIKBUT test, allow approximately 2 minutes for tear film recovery time before attempting another measurement. If the patient accidentally blinks too early or moves causing an incomplete scan, wait approximately 2 minutes before repeating the test. Remind the patient to try to hold open their eye for as long as they can.

[figure not shown]
Figure 4. Completed NIKBUT Examination

Tear Meniscus Height Image Capture

After selecting Tear Meniscus Height from the test menu, select 1.0 zoom and “White” lighting in the Illumination box on the right side of the screen. Adjust the camera focus so that the lower lid tear meniscus is more centrally displayed than it was during the NIKBUT test. Adjust the instrument until the tear meniscus is in best focus. Then instruct the patient to blink. At approximately 2 seconds after the blink, either select “Image” to capture the picture on the screen or press down on the foot pedal. A still image will be captured. Multiple images may be collected as specified in the study protocol.

Figure 5: Complete Tear Meniscus Height Examination

Measuring Tear Meniscus Height on a captured image

Once the image is taken, a new screen will appear. Measurement of tear meniscus height may be performed now, or the image may be reloaded at a later time for analysis. The meniscus height will be measured at the point of the tear film that is straight down from the center of the pupil. To begin a measurement, use the icon indicated by number 3 in Figure 4 to zoom in on the tear film, press the icon 6 times for the proper amount of zoom. Next, select the icon indicated by number 2 in Figure 4. Click on the upper most part of the tear meniscus, then click where the eyelid margin meets the eye. This will

Page 5 of 7

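### At Visits 2 and 4, lens-only fit and lens-surface steps precede the primary NIBUT/NIKBUT reading with no stated recovery time, so pre-measurement handling cannot be separated from the lens effect

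*Combined protocol and SAP*

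**What the plan says.** Section 7.2 sets the order of procedures at each visit. At Visit 2, after visual acuity (2.7), it runs:

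- 2.8, lens fit assessment. An unacceptable fit can rest on limbal exposure, edge lift, excessive movement, or "insufficient movement in all three of the following conditions: primary gaze, up gaze, and Josephson push up".
- 2.9, wettability: "Record the white light lens wettability of both lenses".
- 2.10, lens surface: "Record any front and back surface lens debris & deposits".
- 2.11, the primary measurement, headed "Tear film stability (Pre-Lens or Pre-Corneal as applicable": "Record the first tear film stability (NIBUT/NIKBUT), OD & OS. Record three measurements".

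Steps 2.8 to 2.10 are marked as done only where applicable, and each needs a lens on the eye. Visit 4 has the same order (4.8 to 4.11), with the primary step headed "Tear film stability (Pre-Lens or Pre-Corneal as applicable) as available by site". Neither visit states a rest before the first reading.

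Visit 3 is ordered differently. Step 3.4, "Habitual lens Pre-Lens Tear film stability as available by site", comes before wettability (3.5) and deposits (3.6).

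The work aids set rests between repeated readings. Appendix E (Medmont) asks for at least 30 seconds. Appendix F (Keratograph) tells the examiner to "allow approximately 2 minutes for tear film recovery time before attempting another measurement".

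**The concern.** The primary objective is the within-subject difference in tear film stability between the test lens and spectacles. In the lens condition the eye has just been through gaze changes, lens inspection and possibly a push-up. In the spectacle condition it has not, because the slit-lamp examination there comes after the reading (2.15/4.15). If these steps disturb the film or provoke tearing, the effect falls on one side of the contrast only.

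Randomising the sequence does not help, because the steps go with the lens whichever period it is worn in. The section 14.7 comparison of first-period test-lens data with habitual spectacle wearers has the same imbalance. The study is also unmasked (section 5.2), so a common measurement routine is one of its few protections. At stake is whether a difference reported for the lens is due to the lens alone or partly to what was done to the eye before the reading.

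**Working it through.** **1. The two conditions side by side (Visits 2 and 4)**

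| Step | Test lens | Spectacles |
|---|---|---|
| 2.7 / 4.7 visual acuity | yes | yes |
| 2.8 / 4.8 lens fit | yes | no |
| 2.9 / 4.9 wettability | yes | no |
| 2.10 / 4.10 debris and deposits | yes | no |
| Stated rest before first reading | none | none |
| 2.11 / 4.11 NIBUT/NIKBUT | yes | yes |

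**2. Can the analysis separate the two?** The fixed effects in section 14.5 are lens type, sequence, period, subject group and group by lens type, with age and gender where appropriate. Site and subject are random. An indicator for having had the lens-only steps before the reading would equal the lens-type indicator in every row of the data. The two are completely aliased, so the lens-type estimate is the lens effect plus any handling effect.

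**3. Reproducing the plan's power.** Inputs from section 14.2: variance 34, same-eye correlation across periods 0.5, same-subject correlation across eyes and periods 0.3, 80 eyes, difference 2 s, two-sided 0.05.

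- Variance of one eye's period difference = 2 × 34 × (1 − 0.5) = 34. The across-eye correlation of 0.3 is the same within and across periods, so it cancels from the differences.
- SE = √(34 / 80) = 0.652 s.
- Power at 2 s = 86.6% (normal approximation) or 85.8% (noncentral t, 78 df). The plan states 86%, so its figure is reproduced.

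**4. Illustration of a handling shift.** The documents give no value for a shift *b*, so the values below are assumptions. Each is taken as a constant added to the analysed endpoint in the lens condition. The rejection rate is the two-sided noncentral t probability (78 df) with noncentrality (true difference + *b*) / 0.652.

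| Assumed size of *b* | No true difference | True difference 2 s, *b* opposing |
|---|---|---|
| 0 s | 5.0% | 85.8% |
| 0.25 s | 6.7% | 75.5% |
| 0.5 s | 11.8% | 62.3% |
| 1.0 s | 32.8% | 32.8% |

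Sections 2.2 and 14.5 do not say how the three readings are combined. If they were averaged and only the first were disturbed, a 1.0 s disturbance would shift the endpoint by 1.0 / 3 = 0.33 s, which lies between the second and third rows.

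**The case against.** The step order itself is not in dispute. Several stronger readings are tempting, and the documents do not support them.

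- **A push-up before every lens reading.** A reader might infer this from step 2.8. The push-up appears only within a criterion that needs insufficient movement in all three conditions. A lens that moves adequately in primary or up gaze cannot meet it, so no push-up is then needed. The detailed fitting procedure in Appendix D is redacted, so routine use can be neither shown nor excluded.
- **Two slit-lamp inspections under bright light.** Steps 2.9 and 2.10 name no slit lamp. The package insert uses the biomicroscope for fit and deposits, but it is general labelling and does not cover wettability.
- **The appendices require a recovery period here.** They do not. Their rests apply between break-up readings, in which the subject holds off blinking for as long as possible. They show that the film is treated as needing time to recover from that, and say nothing about rest after lens inspection.
- **Visit 3 is a full precedent.** It is one for wettability and deposits only. No fit assessment precedes or follows step 3.4 for the habitual lens.
- **The results will be biased.** The documents show that handling could enter the contrast. They do not show that it shifts NIBUT.

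There are also mitigating features. Wettability and deposit recording come between any push-up and the reading. Subjects blink normally during Medmont alignment and make two full blinks before a Keratograph recording. The second and third readings follow a rest, so a brief disturbance could fade. Comparing a pre-lens with a pre-corneal film is intended and is no defect. Section 2.3 calls the study a pilot with exploratory hypotheses.

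All of this limits how large the problem is likely to be. None of it gives the two conditions the same route to the first reading. Pilot status does not settle the matter either, since section 14.5 plans a formal test of this contrast with a 95% confidence interval.

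**Conclusion.** The point holds as an avoidable imbalance in the measurement routine. At Visits 2 and 4, steps done only with the lens precede the primary reading without a stated recovery time, and the spectacle condition has no counterpart. The design and model cannot separate any effect of those steps from the lens effect.

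The order and the aliasing follow directly from sections 7.2 and 14.5. The size and direction of any effect are unknown. The false-positive rates of about 7%, 12% and 33% rest on assumed constant shifts of 0.25, 0.5 and 1.0 s and on the plan's variance and correlation. They show how sensitive the test would be and are not evidence that a shift exists. The plan's 86% power is not in question.

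The change is worth making because it is cheap and removes a treatment-linked difference ahead of the primary endpoint.

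**What to change.** At Visits 2 and 4, move tear film stability (2.11/4.11) to directly after visual acuity (2.7/4.7) and before lens fit, wettability and deposits (2.8–2.10/4.8–4.10). Both conditions then reach the primary reading by the same steps. Visit 3 already follows this order for wettability and deposits. NIBUT involves no contact and no dye (Appendix E), so taking it earlier adds no staining or touch before the lens assessments. If the order has to stay, a common stated rest before the first reading in both conditions is the weaker alternative.

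Cost: the procedure steps and eCRF pages are reordered, and lens-surface grading, which is not a primary or secondary endpoint, then follows the tear film readings. There are no added procedures, visits or subjects, and the sample size inputs and the 86% power are unchanged.
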